### **1.3 Trehalose Therapeutic Rationale**

#### *1.3.1 Rationale for the study*

The nonclinical data generated to date for trehalose support its potential to be used as an effective treatment for ALS. Through its effects on reducing proteinaceous aggregates/inclusions promoting autophagy and lysosomal pathways and reducing cell death, trehalose improved muscle strength and overall motor skills in animal models of OPMD, SCA3, and ALS. The clinical safety profile of trehalose and the nonclinical toxicology data support the investigation of trehalose as a potential treatment of ALS.

#### *1.3.2 Rationale for the Dose, Dosing Regimen, and Route of Administration*

**Error! Reference source not found.** If administered orally < 0.5% of ingested trehalose is absorbed into the blood stream. Therefore, to achieve therapeutic blood levels of trehalose, it is necessary to circumvent the metabolism in the human gastrointestinal tract. As such, Seelos has

developed SLS-005 an IV formulation of trehalose for injection, 90.5 mg/mL to be evaluated in this study.

In the single ascending dose study of IV trehalose in healthy subjects, the mean weight in the 54 g dose cohort was 74.5 kg. At the dose of 54 g, subjects received 0.72 g/kg. The area under the curve to time infinity ( $AUC_{inf}$ ) at that dose was  $8,595 \pm 2,575$  hour  $\times$   $\mu$ g/mL. Since clearance is dependent on body weight (i.e., clearance increases with increasing body weight), in order to achieve a consistent exposure in, at, or near the exposure at the MTD, 54 g/1 hour, a weight-based dose of 0.75 g/kg should achieve an exposure within the clinically acceptable safety range.

One of the proposed mechanisms of action of trehalose is to activate autophagy, the blockade of glucose receptors results in a starvation scenario within the cell (DeBosch 2016). Therefore, the MTD will be used to ensure significant exposure. Weekly dosing of IV trehalose is the only regimen to be evaluated in clinical trials to date (patients with OPMD and SCA3) and will be used in this trial.

### *1.3.3 Rationale for the Patient Population*

The pathologic hallmark of the disease is aggregation of proteinaceous inclusions in motor neurons. The main composite of these inclusions is misfolded TDP43 (especially the phosphorylated form), which accumulates in the cytoplasm and is depleted in the nucleus. Patients with either sporadic or familial ALS accumulate TDP43 and patients with the SOD mutation accumulate SOD aggregates and thus have the potential to benefit from treatment with trehalose through activation of autophagy.

## 2. OBJECTIVES

### 2.1 Study Objectives and Endpoints

#### Primary Efficacy Objective:

To evaluate the efficacy of trehalose injection, 90.5 mg/mL for intravenous infusion as compared to placebo on ALS disease progression.

#### Secondary Efficacy Objective:

- To evaluate the effect of trehalose injection, 90.5 mg/mL for intravenous infusion on selected secondary measures of disease progression, including survival.

#### Safety Objective:

- To evaluate the safety of trehalose injection, 90.5 mg/mL for intravenous infusion for patients with ALS.

#### Exploratory Efficacy Objective:

- To evaluate the effect of trehalose injection, 90.5 mg/mL for intravenous infusion on selected biomarkers and endpoints.

#### Primary Efficacy Endpoint:

Change in disease severity as measured by the ALS Functional Rating Scale-Revised (ALSFRS-R) total score using a Bayesian repeated measures model that accounts for loss to follow-up due to mortality.

#### Secondary Efficacy Endpoints:

- Change in respiratory function as assessed by slow vital capacity (SVC).
- Change in muscle strength as measured isometrically using hand-held dynamometry (HHD) and grip strength.
- Survival.

#### Safety Endpoints:

- Treatment-emergent adverse and serious adverse events.
- Changes in laboratory values and treatment-emergent and clinically significant laboratory abnormalities.
- Changes in ECG parameters and treatment-emergent and clinically significant ECG abnormalities.
- Treatment-emergent suicidal ideation and suicidal behavior.

#### Exploratory Efficacy Endpoints:

- Changes in the biofluid biomarkers of neurodegeneration specified in the SOA.
- Changes in the patient reported outcomes specified in the SOA.

### **3. RSA DESIGN**

This study is a multi-center, randomized, placebo-controlled trial, testing active dose of trehalose injection, 90.5 mg/mL for intravenous infusion (0.75 g/kg), given weekly versus placebo.

Participants will be randomized 3:1 active: placebo.

#### **3.1 Scientific Rationale for RSA Design**

This RSA is designed to correspond with the design of the Master Protocol and the goals of the HEALEY ALS Platform Trial.

#### **3.2 End of Participation Definition**

A participant is considered to have ended his or her participation in the placebo-controlled period of the Regimen if they:

- Complete planned placebo-controlled period visits, as described in the SOA, including participants on or off study drug
- Early terminate from the study and complete the Early Termination Visit and Follow-Up Phone call as described in Section 6.9
- Withdraw consent to continue participation in the study, or are lost to follow-up

If a participant initiates open-label study drug in the OLE period, he or she is considered to have completed his or her participation in the OLE period of the Regimen if they choose to discontinue participation or if all planned OLE period visits, including the last visit or the last scheduled procedure shown in the SOA, have been completed.

#### **3.3 End of Regimen Definition**

The end of the placebo-controlled treatment period in a Regimen occurs when all randomized participants have completed their participation in the placebo-controlled period as defined in section 3.2.

The end of the OLE period in a Regimen occurs when all participants who initiated open-label investigational product in the OLE period have completed their participation in the OLE period as defined in section 3.2.

## **4. RSA ENROLLMENT**

### **4.1 Number of Study Participants**

Approximately one hundred-sixty (160) participants will be randomized to this Regimen.

### **4.2 Inclusion and Exclusion Criteria**

In order to be assigned to a Regimen, participants must meet the Master Protocol eligibility criteria. In addition, participants meeting all of the following inclusion and exclusion criteria will be allowed to enroll in this Regimen:

#### *4.2.1 RSA Inclusion Criteria*

There are no additional RSA Inclusion Criteria from those described in the Master Protocol.

#### *4.2.2 RSA Exclusion Criteria*

1. Current diagnosis or healthcare professional-recommended treatment (medication, exercise or diet) of diabetes mellitus
2. Master Protocol screening glucose  $\geq$ 140 mg/dl
3. Prior treatment with IV trehalose or known hypersensitivity to trehalose
4. Current use of oral trehalose (see prohibited medication Section 5.9)
5. Inability for participant to return to site for weekly drug administration, until approved for home infusions
6. Master Protocol screening body weight >144 kilograms

### **4.3 Treatment Assignment Procedures**

Each participant who meets all eligibility criteria for the Regimen will be randomized to receive either 0.75 g/kg of trehalose or equivalent weight-based volume of placebo by weekly intravenous infusion in the study's 24-week placebo-controlled treatment period.

### **4.4 Open Label Extension Eligibility**

Participants who complete the 24-week placebo-controlled treatment period on active or placebo study drug will be eligible to participate in the OLE.

## 5. INVESTIGATIONAL PRODUCT

### 5.1 Investigational Product Manufacturer

The investigational product is SLS-005 (trehalose injection, 90.5 mg/mL for intravenous infusion). This solution for IV infusion is administered once a week at a planned dose of 0.75 g/kg.

Trehalose is a stable, non-reducing disaccharide with 2 glucose molecules linked in an alpha 1,1 configuration. It contains no less than 97.0% and no more than 102.0% of C12H22O11, calculated on the anhydrous basis.

Trehalose Injection 90.5 mg/mL (an aqueous, sterile solution for IV infusion) is provided as a clear liquid in a 300 mL infusion bag. Each 300 mL bag contains 27.15 g of trehalose. See the IB for further details on trehalose.

Placebo is a sodium chloride injection, 0.9%, USP for intravenous infusion, provided as a clear liquid in a 300 mL infusion bag. Placebo is administered once a week in an equivalent weight-based volume as described for trehalose dosing.

### 5.2 Labeling, Packaging, and Resupply

Trehalose will be provided in a 1 bag per kit configuration. Further details are provided in the Pharmacy Manual.

Placebo will be provided in a 1 bag per kit configuration. Placebo has been manufactured by the drug product manufacturer in the same container closure (300-mL freeflex IV bag).

### 5.3 Acquisition, Storage, and Preparation

#### Acquisition

Prior to study treatment, study drug will be supplied to the study site's pharmacy by the Sponsor or its designee.

Shipment of study drug supplies for the study will be accompanied by shipment records describing the contents of the shipment, drug information, and other appropriate documentation. The shipment form will assist in maintaining current and accurate inventory records.

The investigator must ensure the acknowledgement of receipt of the clinical trial material at the site, including that the material was received in good condition.

#### Study Drug Storage

The investigational drug and matching placebo will be stored in the study site's pharmacy, at room temperature (20 to 25 °C) with excursions permitted 15 to 30 °C. The Sponsor or its designee should be notified for any deviation from the storage conditions.

#### Study Drug Preparation

Trehalose Injection 90.5 mg/mL (an aqueous, sterile solution for IV infusion) is provided as a clear liquid in a 300 mL infusion bag containing 27.15 grams of trehalose. No preparation is required for administration of the study drug.

Placebo is also provided as a clear liquid in a 300 mL infusion bag. No preparation is required for administration of placebo.

The dose of IV trehalose or placebo will be calculated based on participant body weight to determine the volume administered to each participant. Each participant's weight should be measured consistently at each in-clinic visit. Shoes and heavy winter clothes (e.g. coats, sweaters, boots) should be removed prior to weighing. If shoes cannot be removed, then weight should be assessed with the participant's shoes on at each clinic visit. Doses are adjusted based on changes in body weight (2 kg increase or decrease) noted during clinical trial assessments. More than 1 bag may be needed per infusion based on the participant's body weight. The intended SLS-005 total infusion time, excluding interruptions, is 60 minutes for infusion volumes up to 2 bags (i.e. up to 600mL) and should not exceed 70 minutes. For patients who require more than 2 bags (i.e. >600mL) of study drug the intended SLS-005 total infusion time should be increased to 90 minutes and not exceed 100 minutes. Management of deviations/excursions is described in the Study Drug MOP.

#### **5.4 Study Medication/Intervention, Administration, Escalation, and Duration**

The participant will receive weekly infusions of study drug (trehalose or placebo). Although for most participants the total infusion time of SLS-005 is set at 60 minutes (+ 10 minutes), participants who require more than 2 bags of study drug the infusion time should be increased to 90 minutes (+10 minutes) throughout the study. All infusions will be administered using an infusion pump and will be followed with an IV flush. The start calendar date and 24-hour clock time as well as the end calendar date and 24-hour clock time of each infusion will be recorded in the study database. If an infusion is interrupted due to infusion issues, i.e. loss of IV site, the infusion can be completed once access has been re-established unless > 30 minutes have elapsed. If 30 or more minutes have elapsed the infusion should not be restarted, and the volume infused prior to the interruption recorded in the CRF as the total dose administered.

If needed the use of an implanted venous access device (e.g. Mediport, PICC) or percutaneous indwelling catheter is permitted however small caliber indwelling catheters in peripheral vessels should only be inserted for single use. Participants are to be monitored for administration site reactions during study drug administration. Infusion site reactions or infusion reactions are to be recorded as AEs using the appropriate coding terms on the eCRF.

If needed, remote services such as infusions at home can be considered after the participant has completed at least 4 weeks of in-clinic infusions, as long as the participant has had no adverse reaction to the infusions and all safety assessments are within acceptable limits. Decision to permit home infusions is at the discretion of the site investigator. Participants approved by their site investigator for weekly infusions outside of the study site will still be required to attend on-site study visits at Week 16 (unless completed remotely due to pandemic-related or other reasons) and 24, and their associated IP infusions at these timepoints can be done in-clinic following completion of the study visit. Telephone visits at Weeks 2, 12 and 20 may be conducted in clinic if the participant is receiving their weekly infusions at the study site and the infusion will occur during the visit window.

#### **5.5 Justification for Dosage**

Based on the preclinical and clinical safety and PK data trehalose injection 90.5 mg/mL should be dosed using a weight-based dosing up to a maximum of 0.75 g/kg. Participants should receive trehalose injection 90.5 mg/mL over 60 + 10 minutes, with the exception noted above for more than 2 bags, using an infusion pump.

## 5.6 Dosage Changes

If for any reason a participant is unable to receive a full dose this should be documented as per participant compliance. Doses are adjusted (increased or decreased) based on a weight change of 2kg or greater from the previous in-clinic volume. A dosing chart, with the volume of study drug to be administered based off body weight to achieve a dose of 0.75 g/kg, is included in the Study Drug MOP.

## 5.7 Participant Compliance

Participants should be encouraged not to miss infusions if at all possible, as it may affect the efficacy of the drug. The dosing window is 1 week  $\pm$  3 days. There should be no fewer than 4 days between study drug infusions.

Compliance will be automatically calculated in the EDC for each weekly infusion.

## 5.8 Drug Returns and Destruction

At each in person visit the steps outlined in the Manual of Procedures must be followed for study drug accountability and compliance, as well as study drug return and destruction.

## 5.9 Overdose

Certain safety events that occur in association with investigational product may require reporting. These safety events include, but are not limited to, the following:

- Overdose of the investigational product, where ‘overdose’ is defined as  $> 125\%$  of the intended dose for a single treatment day infusion.
- Suspected abuse/misuse of the investigational product
- Inadvertent or accidental exposure to the investigational product
- Medication error involving study drug (with or without participant exposure to the investigational product, e.g., name confusion)
- The half-life of Trehalose Injection 90.5 mg/mL is approximately 1.5 hours, and there is no antidote. Trehalose is metabolized to 2 glucose molecules, there are no other metabolites. Supportive care with monitoring of vital signs, blood glucose levels, and liver enzymes should be considered. In 1 subject who received 81 g of Trehalose Injection 90.5 mg/mL, there was an increase in liver enzyme levels, but liver function remained normal and liver enzyme values returned to normal without treatment.

These safety events should be reported to the Coordination Center whether they result in an AE/SAE or not. Safety events associated with an AE/SAE should also be reported in the EDC. The SI should also contact the Medical Monitor within 24 hours of the SI’s awareness.

## 5.10 Prohibited Medications

To date, there are no known pharmacokinetic drug interactions with trehalose. Participants must not take the following medications while on study drug in Regimen E:

- Oral trehalose is not permitted during the study.

## **5.11 Trehalose Known Potential Risks and Benefits**

### *5.11.1 Known Potential Risks*

The safety profile from previous clinical trials of IV trehalose in adults shows no drug-related AEs other than mild, transient glycosuria which was asymptomatic and only 1 SAE, elevated liver enzymes, was considered possibly related to study drug due to temporal association of the changes and lack of alternative causation, however the event resolved without any intervention.

Risks of study participation also includes the risk of an infusion reaction or infusion site reactions. There have been no infusion reactions to date in patients administered IV trehalose; however, 1 patient had an infusion site reaction (erythema). Toxicology data suggests that small indwelling catheters may result in vessel changes after multiple infusions. The inflammatory reaction noted was not associated with any generalized inflammation and there was no organ toxicity, thus it was considered a procedural complication of the indwelling catheter. If needed the use of an implanted venous access device (i.e. Mediport, PICC) or percutaneous indwelling catheter is permitted however small caliber indwelling catheters in peripheral vessels should be single use. Additional risks include those risks related to venipuncture (e.g., hematoma, bleeding, pain, infection), which are low, and the risk of progression of disease for patients assigned to receive placebo.

### *5.11.2 Known Potential Benefits*

Given the relatively benign safety profile of trehalose noted thus far, and the lack of a highly effective treatment for ALS, treatment with trehalose for its potential to arrest or slow progression of ALS disease symptoms is justified.

## 6 REGIMEN SCHEDULE

In addition to procedures in the Master Protocol, the following regimen-specific procedures will be conducted during the study:

- ALSAQ-40
- CNS Bulbar Function Scale
- Serum PK parameter estimates
- CSF biomarker LC3-II and Neurofilament light chain
- HbA1c as part of the clinical safety labs

Participants may be required to re consent to the regimen if new procedures or information is added in the future. Should a participant need to re consent, this should occur during the participant's next in-person visit. If the participant's next in-clinic visit is conducted remotely, re consent may also be completed remotely using the following procedures:

1. The site staff sends copy of the informed consent form to the participant.
2. The participant reads through the consent form but does not sign.
3. The Site Investigator, or other study staff member approved and delegated to obtain informed consent, calls the participant and reviews the informed consent form with the participant over the phone or via telemedicine.
4. The participant signs the informed consent form and mails the original signed consent form back to the site.
5. Once received at the site, the individual who consented the participant via phone signs the informed consent form.

### ***Modifications to Regimen Schedule***

Designated visits in the Schedule of Activities (i.e. Week 16) may be conducted via telemedicine (or phone if telemedicine is not available) with remote services instead of in-person if needed to protect the safety of the participant due to a pandemic or other reason. If a planned in-clinic visit is conducted via telemedicine (or phone if telemedicine is not available) with remote services, only selected procedures will be performed. Instructions on how to document missed procedures are included in the MOP.

In addition to the procedures in the Master Protocol that should be conducted during the phone or telemedicine and remote visits, the following regimen-specific procedures should be completed:

- CNS Bulbar Function Scale

Details on collection of the CNS Bulbar Function Scale, dispensing IP during remote visits, and documenting subjects' willingness to participate in OLE are described in the MOP.

### **6.1 Baseline Visit**

This visit will take place on Day 0. The following procedures will be performed for the regimen schedule:

- ALSAQ-40
  - CNS Bulbar Function Scale
  - Collect safety labs including for HbA1c evaluation
  - Collect urine, *prior to start of infusion*. If urine cannot be collected prior to infusion, no urine should be collected at this visit
  - Confirm dosing volume based off Master Protocol Screening Visit weight
  - Administer first infusion of study drug in clinic *after* all Baseline procedures have been completed
- During each infusion, vital signs associated with the infusion (systolic and diastolic pressure, respiratory rate, and heart rate) are to be measured pre-infusion, 30 minutes ( $\pm$  5 mins) after the start of infusion (SOI), at the end of infusion ( $\pm$  10 mins), and 90 minutes ( $\pm$  10 mins) after the start of infusion. If a participant requires a 90-minute infusion duration due to receiving more than 2 bags of study drug an additional vital signs measurement is to be completed approximately 30 minutes ( $\pm$ 10 mins) after the end of the 90-minute infusion.
    - For applicable participants, collect PK blood sample (Pre-dose, 1-hour  $\pm$  5 minutes, 2 hours  $\pm$  5 minutes, and 4 hours  $\pm$  5 minutes post start of infusion)

[figure not shown]

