		-42 to -1 Days 	-41 to 0 Day 	Day 0	Day 14 ±3	Day 28 ±7	Day 56 ±7	Day 84 ±3	Day 112 ±7	Day 140 ±3	Day 168 ±7	28 days after last dose ±3 days
Biomarker Urine Collection 	Master			X			X		X		X	
PK Blood Collection 	Regimen			X			X					
DNA Collection  (optional)	Master			X								
CSF Collection (optional)	Master			X					X 			
Concomitant Medication Review	Master	X	X	X	X	X	X	X	X	X	X	
Adverse Event Review 	Master	X	X	X	X	X	X	X	X	X	X	X
Document changes in health, medications, and infusion-related adverse events	Regimen				Weekly in conjunction with study drug administration from week 1 through week 24							
Columbia-Suicide Severity Rating Scale	Master			X		X	X		X		X	
Assignment to the Regimen	Master	X										
Randomization within the Regimen	Master		X									
Adjust Dose as Needed 	Regimen					X	X		X		X 	
Administer/Dispense Study Drug	Master			X 	Weekly IV infusion from week 1 through week 24						X 	
Drug Accountability/Compliance	Master				Weekly in conjunction with study drug administration from week 1 through week 24 						X	
Exit Questionnaire	Master										X	
Vital Status Determination 	Master										X	

- 1 Master Protocol Screening procedures must be completed within 42 days to 1 day prior to the Baseline Visit. The Regimen-Specific Screening Visit and Baseline Visit should be combined, if possible.
- 2 During the Master Protocol Screening Visit, participants will be consented via the Platform Trial informed consent form (ICF). After a participant is randomized to a regimen, participants will be consented a second time via the regimen-specific ICF.
- 3 At the Regimen Specific Screening Visit, participants will have regimen-specific eligibility criteria assessed.
- 4 Vital signs include weight, systolic and diastolic pressure, respiratory rate, heart rate and temperature. Height measured at Master Protocol Screening Visit only. If an infusion will occur at the completion of the visit, vital signs should be collected within 30 minutes of the start of infusion to serve as the pre-infusion vital signs collection.

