- 13 Visit may be conducted via phone or telemedicine with remote services instead of in-person if this is needed to protect the safety of the participant due to a pandemic or other reason.
- 14 If required due to pandemic-related restrictions, Forced Vital Capacity (FVC) performed by a Pulmonary Function Laboratory evaluator or with a study-approved home spirometer, or sustained phonation using a study approved method may be used for eligibility (Master Protocol Screening ONLY).
- 15 Master Protocol Screening and Regimen Specific Screening visit windows are relative to Baseline (Day 0).
- 16 Participants completing the PK collection will have blood collected for PK analysis at Baseline (Day 0) and Week 8 (Day 56) at the following time points: pre-dose and 1 hour  $\pm 5$  minutes, 2 hours  $\pm 5$  minutes, and 4 hours  $\pm 5$  minutes post start of infusion (SOI). At each time point, 4mL of blood will be collected.
- 17 All urine samples must be collected prior to IP administration.
- 19 Dose is adjusted only for those participants continuing into the OLE.
- 20 The weight collected during each in clinic visit will be used to calculate the participant's dose. The participant will remain on a stable dose until the next in clinic visit (Weeks 4, 8, 16) when weight be collected, at which point the dose may be adjusted if the participant's weight has increased or decreased by 2kg. Additional information on dose adjustments is included in section 5.6 Dosing Changes.
- 21 If the participant receives an in-clinic infusion within the visit window, this visit may be conducted while the participant is in clinic for their weekly infusion.
- 22 Drug accountability will not be done at phone visits. Compliance will be automatically calculated in the EDC.

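### The first dosing volume is taken from a screening weight up to 42 days old, although weight is measured again at Baseline and no step applies it until Week 4

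*Protocol*

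**What the plan says.** The protocol addresses the weight behind the first dose in several places.

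- Section 6.1 (Baseline Visit) lists, for Day 0: "Confirm dosing volume based off Master Protocol Screening Visit weight". Footnote 1 of the Schedule of Activities places Master Protocol Screening between 42 days and 1 day before Baseline.
- Footnote 20 of the placebo-controlled schedule says: "The weight collected during each in clinic visit will be used to calculate" the participant's dose. Its marker is on the Baseline column header. The same footnote then holds the dose stable until the next in-clinic visit and names Weeks 4, 8 and 16. SAP Section 2.9 carries the same footnote and the same marker.
- The Vital Signs row has an entry at Baseline, and footnote 4 confirms that weight is included: "Vital signs include weight, systolic and diastolic pressure" and the remaining measures.
- The row "Adjust Dose as Needed" has entries at Weeks 4, 8, 16 and 24 (Week 24 only for those entering the open-label extension). The Baseline cell is empty. The sections for Weeks 4/8, 16 and 24 each contain an adjustment step; Section 6.1 does not.
- Section 5.3 (Study Drug Preparation) gives a general rule: "Doses are adjusted based on changes in body weight (2 kg increase or decrease) noted during clinical trial assessments". Section 5.6 has doses changed "based on a weight change of 2kg or greater from the previous in-clinic volume".
- Section 5.5 has trehalose "dosed using a weight-based dosing up to a maximum of 0.75 g/kg", and Section 1.1 gives 0.75 g/kg as the maximum tolerated dose.

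**The concern.** Section 6.1 and footnote 20 point to different weights for the same infusion. If 6.1 is taken as the specific rule for Day 0, the conflict can be resolved, but a gap remains: the site has a current weight in hand and no scheduled step compares it with the screening weight. Section 5.6 does not fill the gap, because before the first infusion there is no previous in-clinic volume to compare with.

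Two things are at stake. The planned dose is already the stated maximum, so a participant who has lost weight since screening starts above it, at first exposure and, for those in the PK subset, at the Baseline PK sampling. And sites following different parts of the protocol can give the same participant different volumes. For a participant whose two weights lie on either side of the two-bag limit, the infusion time differs as well.

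**Working it through.** **Inputs from the documents:** dose 0.75 g/kg weekly; concentration 90.5 mg/mL (300 mL × 0.0905 g/mL = 27.15 g per bag, as Section 5.1 states); adjustment threshold 2 kg (5.3, 5.6); Week 4 visit on Day 28 ± 7; infusion over 60 minutes up to 600 mL and 90 minutes above that (5.3); overdose defined as more than 125% of the intended dose (5.9).

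**Assumed:** a change of 2 to 4 kg between screening and Baseline, at screening weights of 50, 75 and 100 kg. The documents give no data on weight change.

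**Infusions affected.** With weekly dosing from Day 0, the infusions before a Week 4 visit on Day 28 fall on Days 0, 7, 14 and 21, which makes four. A visit on Day 21 gives three, and one on Day 35 gives five.

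**Dose relative to 0.75 g/kg** = screening weight / Baseline weight:

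| Screening weight | 2 kg loss | 4 kg loss | 2 kg gain | 4 kg gain |
|---|---|---|---|---|
| 50 kg | 50/48 = 1.042 | 50/46 = 1.087 | 50/52 = 0.962 | 50/54 = 0.926 |
| 75 kg | 75/73 = 1.027 | 75/71 = 1.056 | 75/77 = 0.974 | 75/79 = 0.949 |
| 100 kg | 100/98 = 1.020 | 100/96 = 1.042 | 100/102 = 0.980 | 100/104 = 0.962 |

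The highest dose in this range is 0.75 × 50/46 = 0.815 g/kg. A 2 kg change corresponds to 2 × 0.75 = 1.5 g, or 1.5/0.0905 = 16.6 mL.

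**Distance from overdose.** Exceeding 125% needs a Baseline weight below 1/1.25 = 80% of the screening weight, that is, a loss of more than 20%.

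**Cumulative dose.** If four of a nominal 24 infusions are affected and the dose is then corrected, the total rises by 4/24 × 2.74% = 0.46% (75 kg, 2 kg loss) to 4/24 × 8.70% = 1.45% (50 kg, 4 kg loss).

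**Infusion time.** 600 mL × 0.0905 g/mL = 54.3 g, and 54.3/0.75 = 72.4 kg. A participant weighing 74 kg at screening is assigned 74 × 0.75/0.0905 = 613 mL over 90 minutes. At 72 kg on Day 0, the Baseline weight gives 72 × 0.75/0.0905 = 597 mL over 60 minutes.

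**The case against.** The strongest reply is that the text can be read consistently. Section 6.1 is the only instruction specific to the Day 0 volume, screening is itself a clinic visit with a weight, and footnote 20 names Weeks 4, 8 and 16 as the points of change, which agrees with the empty Baseline cell. The SAP footnote adds no separate conflict, since SAP Section 1 ranks the regimen appendix above the SAP on matters outside analysis. This is fair, but it settles which weight governs by leaving the newer measurement unused.

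A second reply is that a correction is already possible: Section 5.3 names no visit, and to confirm a volume may imply a check. That reading is open, but neither Section 6.1 nor the schedule states it, so sites may reasonably differ. The dosing chart in the Study Drug MOP might settle the point; it was not available.

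A third is that the protocol tolerates similar drift. With the oldest permitted screening weight, the Day 21 infusion uses a weight 42 + 21 = 63 days old. The last infusion before Week 16 nominally uses one that is 105 − 56 = 49 days old, and the 12-week gaps in the open-label extension reach 77 days. This stands as a limit on importance. The difference is that later drift has no scheduled in-clinic weighing to reveal it, whereas here the weight is taken on the day of dosing.

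Finally, 0.75 g/kg is not a sharp safety limit. Section 1.3.2 derives it from a fixed 54 g dose averaging 0.72 g/kg, with AUC 8,595 ± 2,575 (a coefficient of variation of 2,575/8,595 = 30%), and the 2 kg rule itself accepts small excesses. This also stands, and it is why the point is one of dose accuracy and consistency and not a safety alarm.

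**Conclusion.** The concern holds. The first volume is based on a weight that may be six weeks old, a current weight is measured and not used, and a general footnote points the other way. Under the assumed 2 to 4 kg change, the dose runs 2.0% to 8.7% above 0.75 g/kg after a loss, or 2.0% to 7.4% below it after a gain, across screening weights of 50 to 100 kg. This lasts about four infusions (three to five across the Week 4 window), and in the examples worked the cumulative dose rises by less than 1.5%.

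The issue is small. Placebo volume follows the same weight, so blinding, the between-arm comparison and the estimand are not affected. The size rests on the assumed weight change, and the unseen MOP could narrow the gap in practice. The change is still worth making, because the planned dose is the stated maximum and the correction costs almost nothing.

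**What to change.** In Section 6.1, calculate the first dosing volume from the Baseline Visit weight. If supply planning needs an earlier figure, keep the screening weight for planning only and apply the existing 2 kg rule to the Baseline weight before the first infusion. Add an entry at Baseline in the dose-adjustment row, and bring footnote 20 in the protocol and SAP, and the MOP dosing chart, into line. Section 5.5 needs no change.

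The cost is wording in three documents. No procedure is added: Baseline weight is already measured before the first infusion, and the bags need no preparation. The downside is an occasional same-day change of pump volume, bag count or infusion time. Four bags cover 1,200 × 0.0905/0.75 = 144.8 kg, so a participant screened near the 144 kg limit who has gained weight could need a fifth bag on Day 0. The same can already happen at Week 4.
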